9.5 Renal safety monitoring

Renal events are defined as one of the following:

- confirmed (after ≥ 24h) increase in serum creatinine of ≥ 25% compared to baseline during normal hydration status
- new onset (≥1+) proteinuria, hematuria or glucosuria; or as a
- doubling in the urinary albumin-creatinine ratio (ACR) or urinary protein-creatinine ratio (PCR) (if applicable).

The following two categories of abnormalities/adverse events have to be considered during the course of the study:

- Serum creatinine triggers that will require follow up and repeat assessments of the abnormal laboratory parameter
- Urine dipstick triggers that will require follow up and repeat assessments of the abnormal laboratory parameter

Table 9-3 Specific Renal Alert Criteria and Actions

| Renal Event | Actions |
|---|--|
| Serum creatinine increase 25 – 49% compared to baseline | Confirm 25% increase after 24-48h Follow up within 2-5 days |
| Serum creatinine increase $\geq 50\%$ compared to baseline | Follow up within 24-48h if possible Consider drug interruption Consider patient hospitalization /specialized treatment |
| Albumin- or Protein-creatinine ratio increase ≥ 2 -fold Albumin-creatinine ratio (ACR) ≥ 30 mg/g or ≥ 3 mg/mmol; New dipstick proteinuria $\geq 1+$ Protein-creatinine ratio (PCR) ≥ 150 mg/g or >15 mg/mmol | Confirm value after 24-48h Perform urine microscopy Consider drug interruption / discontinuation |
| New dipstick glucosuria $\geq 1+$ not due to diabetes | Blood glucose (fasting) Perform serum creatinine, ACR |
| New dipstick hematuria not due to trauma | Urine sediment microscopy Perform serum creatinine, ACR |
| Document contributing factors: co-medication, other co-morbid conditions, and additional diagnostic procedures performed in the CRF | |
| Monitor patient regularly (frequency at investigator's discretion) until one of the following: Event resolution: (sCr within 10% of baseline or protein-creatinine ratio within 50% of baseline) Event stabilization: sCr level with $\pm 10\%$ variability over last 6 months or protein-creatinine ratio stabilization at a new level with $\pm 50\%$ variability over last 6 months. | |

9.6 Pregnancy reporting

To ensure patient safety, each pregnancy in a patient on study drug must be reported to Novartis within 24 hours of learning of its occurrence. The pregnancy should be followed up to determine outcome, including spontaneous or voluntary termination, details of the birth, and the presence or absence of any birth defects, congenital abnormalities, or maternal and/or newborn complications. The study drug must be discontinued, though the patient may stay in the study, if she wishes to do so. All assessments that are considered as a risk during pregnancy must not be performed. The patient may continue all other protocol assessments. Pregnancy must be recorded on a Pharmacovigilance Pregnancy Form and reported by the investigator to the local Novartis Drug Safety and Epidemiology Department. Pregnancy follow-up should be recorded on the same form and should include an assessment of the possible relationship to the Novartis study drug of any pregnancy outcome. Any SAE experienced during pregnancy must be reported on an SAE Report Form.

Pregnancy outcomes must be collected for the female partners of any males who took study treatment in this study. Consent to report information regarding these pregnancy outcomes should be obtained from the mother.

9.7 Early phase safety monitoring

The Investigator will monitor adverse events in an ongoing manner and inform the Sponsor of any clinically relevant observations. Any required safety reviews will be made jointly between medically qualified personnel representing the Sponsor and Investigator. Such evaluations may occur verbally, but the outcome and key discussion points will be summarized in writing (e-mail) and made available to both Sponsor and all Investigator(s). Criteria pertaining to stopping the study/treatment or adapting the study design are presented in [Section 7](#).

The Sponsor will advise the Investigator(s) at all sites in writing (e-mail) (and by telephone if possible) of any new, clinically relevant safety information reported from another site during the conduct of the study in a timely manner.

10 Data review and database management

10.1 Site monitoring

Before study initiation, at a site initiation visit or at an investigator's meeting, a Novartis representative will review the protocol and CRFs with the investigators and their staff. During the study Novartis employs several methods of ensuring protocol and GCP compliance and the quality/integrity of the sites' data. The monitor will visit the site to check the completeness of patient records, the accuracy of entries on the CRFs, the adherence to the protocol and to Good Clinical Practice, the progress of enrollment, and to ensure that study drug is being stored, dispensed, and accounted for according to specifications. Key study personnel must be available to assist the monitor during these visits.

The investigator must maintain source documents for each patient in the study, consisting of case and visit notes (hospital or clinic medical records) containing demographic and medical information, laboratory data, electrocardiograms, and the results of any other tests or assessments. All information on CRFs must be traceable to these source documents in the patient's file. The investigator must also keep the original informed consent form signed by the patient (a signed copy is given to the patient).

The investigator must give the monitor access to all relevant source documents to confirm their consistency with the CRF entries. Novartis monitoring standards require full verification for the presence of informed consent, adherence to the eligibility criteria, documentation of SAEs, and the recording of data that will be used for all primary and safety variables. Additional checks of the consistency of the source data with the CRFs are performed according to the study-specific monitoring plan. No information in source documents about the identity of the patients will be disclosed.

10.2 Data collection

Designated investigator staff will enter the data required by the protocol into the Electronic Case Report Forms using fully validated software that conforms to 21 CFR Part 11 requirements. Designated investigator site staff will not be given access to the EDC system until they have been trained. Automatic validation programs check for data discrepancies and,

by generating appropriate error messages, allow the data to be confirmed or corrected before transfer of the data to the CRO working on behalf of Novartis. The Investigator must certify that the data entered into the Electronic Case Report Forms are complete and accurate. After database lock, the investigator will receive copies of the subject data for archiving at the investigational site.

Data not requiring a separate written record will be defined in the Site Operations Manual and assessment schedule and can be recorded directly on the CRFs. All other data captured for this study will have an external originating source (either written or electronic) with the CRF not being considered as source.

All data should be recorded, handled and stored in a way that allows its accurate reporting, interpretation and verification.

10.3 Database management and quality control

Novartis staff, or CRO working on behalf of Novartis, review the data entered into the eCRFs by investigational staff for completeness and accuracy and instruct the site personnel to make any required corrections or additions. Queries are sent to the investigational site using an electronic data query. Designated investigator site staff is required to respond to the query and confirm or correct the data. If the electronic query system is not used, a paper Data Query Form will be faxed to the site. Site personnel will complete and sign the faxed copy and fax it back to Novartis staff, or CRO working on behalf of Novartis, who will make the correction to the database.

Concomitant medications entered into the database will be coded using the WHO Drug Reference List, which employs the Anatomical Therapeutic Chemical classification system. Medical history/current medical conditions and adverse events will be coded using the Medical dictionary for regulatory activities (MedDRA) terminology.

Laboratory samples will be processed centrally and the results will be sent electronically to Novartis (or a designated CRO).

ECG readings will be processed centrally and the results will be sent electronically to Novartis (or a designated CRO).

Randomization codes and data in reference to dispensing of study drug(s) to the subject and all IRT recorded dosage changes will be tracked using Interactive Response Technology (IRT). The system will be supplied by a vendor, who will also manage the database. The database will be sent electronically to Novartis (or a designated CRO).

Each occurrence of a code break via IRT will be reported to the clinical team and monitor. The code break functionality will remain available until study shut down or upon request of Novartis.

The occurrence of any protocol deviations will be determined. After these actions have been completed and the database has been declared to be complete and accurate, it will be locked and the treatment codes will be unblinded and made available for data analysis. Any changes to the database after that time can only be made by joint written agreement between the COAR Analytics NIBR Franchise Head and the relevant NIBR TA Head.

porate Confidential Information

10.4 Data Monitoring Committee

Not required.

10.5 Adjudication Committee

Not required.

11 Data analysis

The analysis will be conducted on all subject data at the time the trial ends. Any data analysis carried out independently by the investigator should be submitted to Novartis before publication or presentation.

11.1 Analysis sets

For all analysis sets, subjects will be analyzed according to the study treatment(s) received.

The full analysis set will include all subjects that received any study drug.

The safety analysis set will include all subjects that received any study drug. The PK analysis set will include all subjects with at least one valid (i.e. not flagged for exclusion) PK concentration measurement, who received study drug and no protocol deviations with relevant impact on PK data.

The PD analysis set will include all subjects that received study drug and had no protocol deviations with relevant impact on PD data.

11.2 Subject demographics and other baseline characteristics

All data for background and demographic variables will be listed by treatment group and subject. Summary statistics will be provided by treatment group.

Relevant medical history, current medical conditions, results of laboratory screens, drug tests and any other relevant information will be listed by treatment group and subject.

11.3 Treatments

Data for study drug administration (rescue medication) and concomitant therapies will be listed by treatment group and subject.

Summaries and listings of cumulative exposure to study drug (cumulative dose received over the treatment period) will be provided.

11.4 Analysis of the primary variable(s)

The primary aims of this study are to assess safety in patients with pSS and to investigate the effect of CDZ173 on efficacy (as measured by the ESSPRI) at study week 13. The statistical analysis model will include ESSPRI data from all time points up to study week 13 and summaries of safety and tolerability will be provided.

11.4.1 Variable(s)

The primary efficacy variable is the ESSPRI change from baseline.

11.4.2 Statistical model, hypothesis, and method of analysis

It is assumed that the ESSPRI will follow an approximately normal distribution. If this assumption appears not to be met, alternative statistical analysis methods may be applied. These will be described in the Reporting and Analysis Plan (RAP).

The primary efficacy analysis will be based on a longitudinal mixed model of ESSPRI as a function of baseline ESSPRI, baseline intake of steroids (yes/no, which is a stratification factor for the randomization), treatment, time as a continuous variable (linear and quadratic terms), interaction between treatment and time, as well as a random intercept, random slope and random quadratic effects by subject to account for within-subject correlations. An unstructured covariance matrix for the random effects will be fitted along with an independent error matrix. The difference between active treatment and placebo in change from baseline in ESSPRI at study week 13 will be estimated from the model and presented with 80% confidence intervals. Simpler models will also be considered in case the pre-specified model does not fit the data well.

The following criteria will be considered indicative of treatment efficacy:

- Statistically significant decrease in ESSPRI at week 13 visit on treatment compared to placebo (at one-sided 10% level)
- Estimated mean reduction in ESSPRI at week 13 visit of 1 point or more than on placebo (see [Section 3.2](#))

11.4.3 Handling of missing values/censoring/discontinuations

All subjects with a baseline ESSPRI and at least one post-baseline ESSPRI will be included in the primary analysis. The primary analysis method provides unbiased estimates of the treatment effect under the assumption that data are missing at random (MAR). Guidelines for subject discontinuation should ensure that this assumption is reasonable. If a substantial proportion (e.g. more than 15%) of subjects discontinue before week 13 visit, alternative methods to account for missing data may be considered.

11.4.4 Supportive analyses

Simpler models may be considered, including simpler covariance structures. If the time course doesn't appear to be quadratic, time may be modeled as a categorical variable.

11.5 Analysis of secondary and exploratory variables

11.5.1 Efficacy / Pharmacodynamics

Corporate Confidential Information

11.5.2 Safety

Vital signs

All vital signs data will be listed by treatment, subject, and visit/time and if ranges are available abnormalities (and relevant orthostatic changes) will be flagged. Summary statistics will be provided by treatment and visit/time.

ECG evaluations

All ECG data will be listed by treatment, subject and visit, abnormalities will be flagged. Summary statistics will be provided by treatment and visit.

A longitudinal PK-QT model using all available data will be used to see if there is any concentration-dependent increase in QT. This model may include data from other studies exploring CDZ173 and may be reported in a separate report. The model will include a random subject effect to account for the within-patient correlations. In case the direct PK-QT model doesn't fit the data appropriately, alternative models taking into account potential hysteresis will be used.

Clinical laboratory evaluations

All laboratory data will be listed by treatment, subject, and visit and if normal ranges are available abnormalities will be flagged. Summary statistics will be provided by treatment and visit.

Adverse events

All information obtained on adverse events will be displayed by treatment and subject.

The number and percentage of subjects with adverse events will be tabulated by body system and preferred term with a breakdown by treatment. A subject with multiple adverse events within a body system is only counted once towards the total of this body system.

Infections

The frequency of infections will be tabulated.

11.5.3 Pharmacokinetics

The pharmacokinetics of CDZ173 will be evaluated in patients in the PK analysis set.

CDZ173 plasma concentration data will be listed by treatment, subject, and visit/sampling time point. Descriptive summary statistics will be provided by treatment and visit/sampling time point, including the frequency (n, %) of concentrations below the LLOQ and reported as zero.

Summary statistics will include mean (arithmetic and geometric), SD, CV (arithmetic and geometric), median, minimum and maximum. An exception to this is T_{max} where median, minimum and maximum will be presented. Concentrations below LLOQ will be treated as zero in summary statistics and for PK parameter calculations. A geometric mean will not be reported if the dataset includes zero values. Pharmacokinetic parameters will be calculated by non-compartmental methods as described in [Section 8.6](#) and will be listed by treatment and subject.

Corporate Confidential Information

Corporate Confidential Information

11.5.4 Pharmacokinetic / pharmacodynamic interactions

Relationships between exposure and selected PD variables will be explored by a graphical approach and descriptive statistics of exposure and PD variables will be provided. Additional analysis such as exposure-response models will be performed, if warranted.

11.5.5 Other assessments

11.5.5.1 Imaging biomarkers

Corporate Confidential Information

tial Information

11.6 Sample size calculation

A total of approximately 27 patients will be recruited into the study. Patients will be randomized in a 2:1 ratio to either CDZ173 (n=18) or placebo (n=9) treatment groups. This number is based firstly on the assumed treatment effect in the primary endpoint ESSPRI and secondly on an assumed drop-out rate of 10% (i.e. 3 patients).

With 24 patients for the analysis of the primary efficacy variable (16 in the CDZ173 treated group and 8 in the placebo group), the study would have around 10% chance of having a false-positive result, i.e. of meeting both efficacy criteria when the true difference between CDZ173 and placebo is zero ESSPRI points.

The power of the study is 86% (when the true difference between CDZ173 and placebo is 2 points in ESSPRI).

The criteria for success are assumed to be the efficacy criteria defined in [Section 11.4.2](#).

These calculations assume that the change from baseline in ESSPRI is approximately normally distributed with a standard deviation of 2. This estimate of the standard deviation is based on a study of rituximab in patients with pSS ([Meiners et al 2012](#)).

The calculated numbers come from simulations done in R version 3.2.2.

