6.1.3 Statistical model, assumptions and hypotheses

It is assumed that the ESSPRI will follow an approximately normal distribution.

A positive sign of therapeutic effects will be considered to be a reduction of at least 1 point in the change from baseline between CDZ173 and placebo with a moderate level of evidence. Additionally there should be a high level of evidence that is a difference between CDZ173 and placebo. These criteria will be evaluated by calculating Bayesian posterior probabilities as follows:

$\Pr(\theta_{\text{CDZ173,13w}} - \theta_{\text{placebo,13w}} < 0 \mid \text{data}) > 90\%$ and

$\Pr(\theta_{\text{CDZ173,13w}} - \theta_{\text{placebo,13w}} < -1 \mid \text{data}) > 50\%$

where θ means change from baseline in ESSPRI at 13 weeks.

It is assumed that Y_{ijt} , the observed change from baseline in ESSPRI for subject i receiving treatment j (CDZ173 or placebo) at time t , follows a normal distribution $N(\theta_{jt}, \sigma^2)$. It is further assumed that θ_{jt} follows a standard non-informative prior Normal distribution, $p(\theta_{jt}, \sigma^2) = 1/\sigma^2$.

The statistical model will be a repeated measures model fitting terms for treatment by timepoint and baseline by timepoint using the SAS procedure PROC MCMC. Estimates of the difference between CDZ173 and placebo at each timepoint will be derived from this model and presented together with 95% credible intervals. The estimates of the posterior probabilities of the efficacy criteria being met will be provided.

Patients with missing ESSPRI at baseline will not be included in the analysis. Patients with missing data at one or more timepoints post baseline will be included in the analysis. The planned model assumes that missing values are missing at random. The reasonableness of this assumption will be checked during the blinded review of the data and if necessary further methods may be applied.

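### Is the 86% power in Protocol 11.6 wrong for 16 + 8 analysed patients?

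*Protocol*

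**What the plan says.** Protocol 11.6 plans to randomize about 27 patients 2:1 (18 and 9) and allows for 10% drop-out, which leaves 24 for the primary efficacy analysis: "16 in the CDZ173 treated group and 8 in the placebo group". On variability it says: "These calculations assume that the change from baseline in ESSPRI is approximately normally distributed with a standard deviation of 2". Success means meeting the criteria of Protocol 11.4.2. There are two. The first is: "Statistically significant decrease in ESSPRI at week 13 visit on treatment compared to placebo (at one-sided 10% level"). The second asks that the model's week 13 estimate favour CDZ173 over placebo by at least 1 point.

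The section gives a false-positive rate of around 10%, and on power it says: "The power of the study is 86% (when the true difference between CDZ173 and placebo is 2 points in ESSPRI"). On the source of both figures it says only: "The calculated numbers come from simulations done in R version 3.2.2".

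Protocol 11.4.2 does not plan a two-sample test. It plans a longitudinal mixed model with baseline ESSPRI, baseline steroid use, treatment, time and treatment-by-time, using all visits up to week 13. By Table 8-1, ESSPRI is collected at baseline and at weeks 5, 9 and 13 within that span. SAP 6.1.3 later applies a Bayesian form of the two criteria in a repeated-measures model with baseline-by-timepoint terms. It states no power.

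**The concern.** The power sentence comes straight after the one that fixes 16 + 8 as the analysed sample, so a reader will take 86% as the power after drop-out. The usual two-group calculation on the section's inputs does not reach it, although the false-positive rate in the same section does reproduce. In addition, all 27 patients analysed as 18 + 9 give 86.3% with a pooled t-test. That coincidence invites the suspicion that the figure was computed before the drop-out allowance. If so, the chance of missing a true 2-point effect would be about 15% to 17% rather than 14%, and a headline design figure would be slightly too favourable.

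**Working it through.** **Inputs.** From Protocol 11.6: 16 and 8 analysed, SD of change 2, true difference 2. From Protocol 11.4.2: one-sided 10% significance and an estimated difference of at least 1 point, both required.

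**Unadjusted two-group calculation.**

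- Standard error: 2 × √(1/16 + 1/8) = 0.866.
- Smallest significant difference: 1.282 × 0.866 = 1.110 with the normal cut-off, or 1.321 × 0.866 = 1.144 with t on 22 df. Both exceed 1, so at the assumed SD the 1-point criterion adds little.
- Known SD: power = Φ((2 − 1.110)/0.866) = 84.8%.
- With the SD estimated, the 1-point criterion can bind when the sample SD is small, so the two criteria must be evaluated jointly.

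| Method, both criteria | Power at 16 + 8 | False-positive rate |
|---|---|---|
| Known SD | 84.8% | 10.0% |
| Estimated SD, normal cut-off | 84.2% | 9.9% |
| Pooled t, 22 df | 83.3% | 9.5% |
| Welch t | 82.3% | 9.1% |

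The false-positive rates agree with the protocol's figure of around 10%, so the inputs and the success rule have been read correctly. The gap to 86% is 86 − 84.8 = 1.2 points at best and 86 − 83.3 = 2.7 points with the pooled t-test (3.7 with Welch).

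**Baseline-adjusted calculation.** Change is follow-up minus baseline, so it normally correlates with baseline. If baseline and week 13 have equal variances and correlate r, the absolute baseline-change correlation is √((1 − r)/2). Adjustment removes that share of the residual variance. Power was simulated at 16 + 8 with SD of change 2, both criteria, and a t-test adjusted for baseline only:

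| Assumed r | Baseline-change correlation | Power |
|---|---|---|
| 0.8 | √(0.2/2) = 0.32 | 84.6% |
| 0.7 | √(0.3/2) = 0.39 | about 86% |
| 0.6 | √(0.4/2) = 0.45 | 87.4% |
| 0.5 | √(0.5/2) = 0.50 | 88.5% |

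Adding steroid use as a second covariate (assuming 40% users) costs about 1 point. The baseline-change correlation needed for 86% then rises from about 0.38 to about 0.44, which corresponds to r = 1 − 2 × 0.44² = 0.61. The equal variances, r and the 40% are all assumptions. The entry rule of ESSPRI at least 5 at screening could narrow the baseline spread and weaken the gain.

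**Simulation error.** The run count is not given. With an assumed 1,000 runs and a true power of 84.8%, the 95% half-width is 1.96 × √(0.848 × 0.152/1000) = 2.2 points. The chance of a result that rounds to exactly 86% is then 21%, against 3% if the true power is 83.3%. With 10,000 runs the chances are 2.6% and below 0.001%.

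**The case for a change.** The best case for a change is that each route to 86% needs something 11.6 does not supply: a correlation, a small run count, or 18 + 9 as the analysed sample. The section gives only an SD for the change score, which suits an unadjusted calculation. On that calculation 84.8% is the ceiling, and it rounds to 85%. SAP 6.1.3 might seem to point the same way: at a single visit, without covariates, its prior gives a posterior for the difference that is t with 22 df, so its rule becomes the pooled t-test plus the 1-point threshold, at 83.3%. One added sentence would settle the matter cheaply.

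Part of this stands. The model, the correlation and the run count are absent, so the figure cannot be reproduced exactly from the text. The rest does not carry. The SAP model includes baseline-by-timepoint terms, so the equivalence with the unadjusted t-test does not describe the analysis it plans. The match at 18 + 9 depends on the method, since with known SD the same sample gives 87.9%, and nothing in the documents shows that this sample was used. Rewriting the power as 83% to 85% could replace a valid simulated figure with one from a test that neither document plans.

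**Conclusion.** The figure of 86% is not shown to be wrong, and no change follows. Unadjusted two-sample calculations on 16 + 8 give about 83% to 85% (82.3% with Welch), 1.2 to 2.7 points below the stated power for the pooled-t and known-SD versions. The baseline-adjusted analysis that the protocol plans gives 84.6% to 88.5% for assumed baseline-to-week-13 correlations from 0.8 to 0.5, and 86% lies within that range. Simulation error around 84.8% is a further possibility if few runs were used.

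This rests on equal variances at baseline and week 13 and on a correlation the documents do not report. If baseline explained almost none of the change, the planned model would have no such advantage and the stated power would be optimistic by roughly 2 to 5 points, since the adjusted simulations at zero correlation give 81.9% with baseline alone and 80.6% with steroid use added. Even then, the sample size, the analysis and the success criteria would be the same, and the study is declared non-confirmatory. What remains is a simulation described briefly. More detail would help a reader check it but would alter no decision.

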| Efficacy assessments | 
 • EULAR Sjögren's Syndrome Patient Reported Intensity (ESSPRI) • EULAR Sjögren's syndrome disease activity index (ESSDAI) • Short Form (36) Health Survey (SF-36) • Multidimensional Fatigue Inventory (MFI) Questionnaire • Physician's and Patient's assessment of global disease activity (Visual Analog Scale, VAS) Corporate Confidential Information |
| Key safety assessments | 
 • Physical examination • Vital signs • Safety Laboratory(Hematology, Biochemistry, Urinalysis) • Electrocardiogram (ECG) • Adverse Events |
| Corporate Confidential Information | Corporate Confidential Information |

| | |
|----------------------|---|
| Data analysis | 
The primary efficacy analysis will be based on a longitudinal mixed model of ESSPRI as a function of baseline ESSPRI, baseline intake of steroids (yes/no, which is a stratification factor for the randomization), treatment, time as a continuous variable (linear and quadratic terms), interaction between treatment and time, as well as a random intercept, random slope and random quadratic effects by subject to account for within-subject correlations. The difference between active treatment and placebo in change from baseline visit in ESSPRI after 12 weeks treatment will be estimated from the model and presented with 80% confidence intervals. Simpler models will also be considered in case the pre-specified model does not fit the data well.
 
The following criteria will be considered indicative of treatment efficacy:
 
- Statistically significant decrease in ESSPRI after 12 weeks on treatment compared to placebo (at one-sided 10% level)- Estimated mean reduction in ESSPRI after 12 weeks treatment of 1 point or more than on placebo 
The decrease of 1 point is considered clinically relevant as 0.67 – 1 points have been published to be the minimal clinically important improvement. In the absence of a standard of care with demonstrated long-term efficacy, no confirmation is available that a decrease of 1 point will translate into a long-term benefit.
 |
| Key words | CDZ173, PI3K pathway, primary Sjögren's syndrome |

1 Introduction

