3.2 Rationale of study design

CDZ173 is an oral, low molecular weight compound that selectively inhibits the lipid kinase PI3K δ , an important mediator of immune cell activation and germinal center formation. The essential role of PI3K δ in the adaptive as well as the innate immune system strongly supports the rationale for the PI3K δ targeted intervention in autoimmune diseases. The interference with germinal center formation further supports expected efficacy in patients with pSS where ectopic germinal centers in salivary glands are considered pathogenically important. This study will be conducted in patients with active pSS, where no established clinically effective disease modifying treatment has been proven effective against the underlying disease.

A randomized, placebo-controlled, double-blind approach is used to eliminate potential bias in reporting safety and clinical efficacy data. Patients will be randomized to CDZ173 or placebo in a 2:1 ratio in order to minimize exposure to placebo and to gather more data on CDZ173. Stratified randomization is done in order to limit imbalances between active and placebo arms in baseline intake of oral corticosteroids.

After the double-blind period, the patients will enter a follow-up period; for which a duration of 4 weeks was chosen to allow sufficient time for safety monitoring.

In addition to safety, efficacy estimated by the EULAR Sjögren's Syndrome Patient Reported Index (ESSPRI) is chosen as a key endpoint of the study (Seror et al 2011). A decrease of 1.7 points was observed at week 16 in a small open-label study with rituximab (Meiners et al 2012). In a publication the group of Seror reported 0.67 – 1 ESSPRI points to be the minimal clinically important improvement (Seror et al 2016). In addition to the ESSPRI, efficacy estimated by the EULAR Sjögren's Syndrome Disease Activity Index (ESSDAI) is chosen as a second disease specific endpoint of the study. The ESSDAI assesses organ involvement in patients with pSS and has been shown to be sensitive to suggest efficacy of rituximab treatment in a randomized controlled trial (Moerman et al 2014). Further efficacy assessments include diseases-independent outcome variables (SF-36, MFI, patients' and

physicians' global assessments)

Corporate Confidential Information

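### Is the trial underpowered because Protocol 11.6 states power only for a 2-point ESSPRI difference?

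*Protocol*

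**What the plan says.** On the sample size, Protocol 11.6 says: "This number is based firstly on the assumed treatment effect in the primary endpoint ESSPRI". It plans 27 randomised patients (18 and 9) and 24 analysed (16 and 8), with an SD of 2 for the change from baseline. It reports two operating characteristics from simulation: a false-positive rate of around 10% at no true difference, and "The power of the study is 86% (when the true difference between CDZ173 and placebo is 2 points in ESSPRI". The SD has a source: "This estimate of the standard deviation is based on a study of rituximab in patients with pSS". The 2 points have none in the visible text.

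Success means meeting both criteria in Protocol 11.4.2: "Statistically significant decrease in ESSPRI at week 13 visit on treatment compared to placebo (at one-sided 10% level"), and "Estimated mean reduction in ESSPRI at week 13 visit of 1 point or more than on placebo". SAP 6.1.3 restates these as posterior probabilities, above 90% for any benefit and above 50% for a benefit of more than 1 point: "A positive sign of therapeutic effects will be considered to be a reduction of at least 1 point in the change from baseline".

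Two other ESSPRI figures bear on the choice of 2 points. Protocol 3.2 reports: "A decrease of 1.7 points was observed at week 16 in a small open-label study with rituximab". It also cites 0.67 to 1 point as the minimal clinically important improvement. The synopsis says: "The decrease of 1 point is considered clinically relevant".

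**The concern.** The rituximab study that supplies the SD appears in Section 3.2 with an observed fall of 1.7 points. The protocol takes its SD from that study but assumes a larger effect, without a visible reason. The 1.7 has no control group behind it, so a placebo-controlled difference would be smaller still if placebo patients improved. No power is given at 1.7 points or at the 1 point described as clinically relevant.

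What would be at stake is the reading of a negative result. The outcome feeds into further development in this disease. A reader who sees only 86% might take unmet criteria as good evidence against a useful effect. At 2 points the miss rate is 14%, about 1 in 7. At 1.7 points it is roughly 1 in 4, and at exactly 1 point the study fails more often than it succeeds.

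**Working it through.** **Inputs.** From Protocol 11.6: 16 and 8 analysed patients, SD 2, true difference 2 points. From Protocol 11.4.2: one-sided 10% test, and an estimate of at least 1 point. The normal quantile for one-sided 10% is 1.2816.

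**Reproducing the stated 86%.**

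- Standard error: 2 × √(1/16 + 1/8) = 0.866.
- Smallest significant difference: 1.2816 × 0.866 = 1.11 points (1.14 with a t-test on 22 degrees of freedom). This exceeds 1 point, so the second criterion seldom binds at this sample size.
- Power at 2 points, SD known: Φ(2/0.866 − 1.2816) = Φ(1.028) = 84.8%.
- Simulation of both criteria with an unadjusted t-test (400,000 runs): 83.2%, with a false-positive rate of 9.5%.

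The stated 86% corresponds to a standard error of 2/(1.2816 + 1.0803) = 0.847. That is a variance about 4% lower (0.847²/0.866² = 0.956), which a modest gain from baseline adjustment could supply. The figure is sound.

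**Smaller true differences, 16 versus 8.** The formula columns use Φ(d/SE − 1.2816), with SE 0.866 or 0.847.

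| True difference d | Both criteria, t-test (simulated) | SD known | SE scaled to the stated 86% |
|---|---|---|---|
| 0 | 9.5% | 10.0% | 10.0% |
| 0.67 | 29.2% | 30.6% | 31.2% |
| 1.0 | 43.2% | 45.0% | 46.0% |
| 1.7 | 73.4% | 75.2% | 76.6% |
| 2.0 | 83.2% | 84.8% | 86.0% |

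Like for like, moving from 2 to 1.7 points lowers power from 86% to 76.6%, or from 83.2% to 73.4%. That is about 10 percentage points on either basis.

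**Why the 1-point row is low.** Success requires the estimate to reach 1 point. If the truth is exactly 1 point, an unbiased, symmetric estimate falls on the right side half the time. As the sample grows, the significance threshold drops below 1 point, the second criterion takes over, and the success probability approaches 50% without passing it. The SAP rule behaves the same way: with a non-informative prior, a posterior probability above 50% for a benefit beyond 1 point amounts to an estimate beyond 1 point.

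**Would more patients matter?** If all 27 randomised patients were analysed (18 versus 9), the scaled standard error would be 0.847 × √(24/27) = 0.798. Power at 1.7 points would be Φ(1.7/0.798 − 1.2816), about 80%; the unadjusted t-test simulation gives 76.7%. Protocol 11.4.3 analyses everyone with a baseline and one post-baseline ESSPRI, and Protocol 7.5 allows replacement, so the analysed number may exceed 24.

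**What a failed study would show.** The 80% interval has a half-width of 1.2816 × 0.866 = 1.11 points. An estimated benefit of 0.8 points would miss both criteria, yet its interval would run from −0.31 to 1.91 and plainly include 1 point. For the interval to exclude a 1-point benefit, the estimate would have to be below 1 − 1.11 = −0.11, that is, slightly in favour of placebo.

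**The case for a change.** The best argument for a change is that the choice of effect size matters most in an early study, where one result may end a programme. Protocol 11.6 says the number of patients rests first on the assumed effect, and that section has no blacked-out text, yet the reader cannot tell where 2 points came from. The SAP also makes a Bayesian rule primary and moves the protocol's mixed model to a supportive role, and its visible text gives no operating characteristics for that rule. A short table would cost almost nothing.

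Part of this stands. The visible text does not justify 2 points, and a table over several true differences describes a two-criterion rule better than a single power figure.

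The rest is weaker. The 1.7 points is a within-group change on rituximab at week 16, whereas Section 11.6 assumes a difference from placebo for CDZ173 at week 13. The protocol never offers 1.7 as the expected effect, so the comparison is loose. Several background and rationale sections are blacked out, so support for 2 points may exist where it cannot be seen. The Bayesian rule with a non-informative prior closely matches the frequentist one, so the table above should serve for both.

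The risk of over-reading is also limited by the planned reporting. The protocol model gives 80% intervals. The SAP adds 95% intervals to that model, 95% credible intervals to the primary one, and the posterior probability of a benefit beyond 1 point. Both documents call the study non-confirmatory.

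**Conclusion.** No change to the plan follows. The stated 86% is correct to within about 3 percentage points under any reasonable reading of the inputs (83-86%). Power on the same inputs is 73-77% at 1.7 points and 43-46% at 1 point. The first of these uses a benchmark that is not a between-arm difference. The second is a property of a rule that makes 1 point the threshold for success, so the design effect has to lie above 1 point and adding patients could not lift that figure past about 50%.

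These results assume 16 and 8 analysed patients, normally distributed changes with an SD of 2, and an unbiased estimate. A larger SD would lower power at every true difference.

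A power table or a stated reason for 2 points would alter no analysis, result or success rule. SAP 6.2.1 describes a printing fault at one site in the past tense, so the trial was already running when the SAP was written. For a small proof-of-concept study, reporting power at one design effect is a fair trade-off. A sentence in the study report on the choice of 2 points, with success probabilities at smaller differences, would be a useful courtesy to readers but is not a correction.
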